8.3.7. ECG Data

ECG data will be databased and available upon request.

8.3.8. Other Safety Data

None.

8.3.9. Concomitant Treatments

All concomitant medication(s) as well as non-drug treatment(s) will be provided in the listings.

8.3.10. Screening and Other Special Purpose Data

All the screening data will not be brought in-house, and therefore will not be listed.

CCI [REDACTED]
[REDACTED]
[REDACTED]
[REDACTED]

8.3.12. Banked Bio-specimen data

Pharmacogenomic or biomarker data from Banked Biospecimens may be collected during or after the trial and retained for future analyses; the results of such analyses are not planned to be included in the CSR.

9. REFERENCES

None.

10. APPENDICES

Appendix 1. SAS CODE FOR ANALYSES

An example of the PROC MIXED code for Plasma data analysis is provided below:

```
proc mixed data=tab.pk;
  class trt participant;
  model l&var= trt/ ddfm=KR;
  random participant /participant=participant;
  lsmeans trt;
  estimate 'Test vs Reference' trt -1 1 /cl alpha=0.1;
  ods 'Estimates' out=est&var;
  ods 'lsmeans' out=ls&var;
  ods 'covparms' out=cov&var;
  ods 'tests3' out=tst&var;
run;
```

/* Letter assignments for treatments (trt) within the estimate statement above are as follows;

For F:

A = Reference = IV ^{14}C -PF-06865571
B = Test = oral PF-06865571

For Fa:

A = Reference = Total ^{14}C _Urine_IV
B = Test = Total ^{14}C _Urine_PO

*/;

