4.2. Scientific Rationale for Study Design

This study will investigate the ADME of $[^{14}\text{C}]$ PF-06865571 and characterize plasma, fecal and urinary radioactivity and identify any metabolites, if possible, of $[^{14}\text{C}]$ PF-06865571 in male participants (obtained from Periods 1 and 2). A 2-period design is being used to minimize variability and enable within -participant comparison of the urinary excretion of radioactivity with both routes for the estimation of Fa. Only male participants will be enrolled to also minimize variability. Only nonsmokers will be enrolled to minimize any potential effect on metabolism by smoking. In addition, this study will provide a better understanding of the PK disposition of PF-06865571 by obtaining IV clearance and delineating the extent of oral absorption (F and Fa), further assisting with BCS classification assessment for PF-06865571. This information will support the further formulation development. Oral dosing will be administered with a meal as food has been shown to significantly increase exposures of PF-06865571 and mimics how PF-06865571 is being administered in the clinical program.

Period 2 of this study will enable assessment of F for PF-06865571. F will provide information on the amount of PF-06865571 reaching the systemic circulation. Determination of the Fa (obtained from Periods 1 and 2) will provide information on the fraction of the total PF-06865571 dose absorbed, regardless of the fate of that dose after absorption (ie, metabolism, degradation, etc). Since F is dependent on Fa, Fg and Fh, characterization of

both F and Fa will enable determination of the first pass effect. Therefore, the study will aim to characterize both F and Fa.

In order to achieve sufficient bioanalytical sensitivity for the microtracer dose and differentiate the plasma concentrations resulting from the radiolabeled IV dose and those resulting from the oral dose, an ultra-sensitive AMS method will be used to quantify plasma concentrations of radiolabeled parent drug as well as total ^{14}C derived from the microtracer dose based on measurement of ^{14}C .⁸ PF-06865571 will be considered highly permeable if either F or Fa is greater than 0.85 (as per BCS guidance).⁹

CCI

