9.2. Sample Size Determination

A sample size of 6 male participants has been chosen based on the industry standard sample size for ADME Mass Balance studies and radiolabeled tracer studies. This sample size was not chosen based on any empirical data or hypothesis testing criteria.

Participants who withdraw from the study, for non-safety reasons, may be replaced if the number of participants with evaluable data is less than 4.

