2.1. Study Design

This study is a Phase 1, open-label, non-randomized, 2-period, fixed-sequence, single-dose study of PF-06865571 in healthy male participants to characterize the ADME properties of $[^{14}\text{C}]$ PF-06865571 following oral administration; and to evaluate the absolute oral bioavailability (F) and fraction absorbed (Fa) of PF-06865571 following oral administration of unlabeled PF-06865571 and IV administration of $[^{14}\text{C}]$ PF-06865571.

In this study, 6 participants will be enrolled to ensure evaluable data is acquired in at least 4 participants. Each participant will receive 2 regimens (A and B) in Periods 1 and 2, respectively, as outlined in Figure 1. Participants who withdraw from the study may be replaced if the number of evaluable participants is less than 4.

Figure 1. Two Period Fixed Sequence Study Design

* Completion of Period 1 (1 participant at a time) when at least 1 of 3 criteria are met: (1) $\geq 90\%$ of radioactive dose has been recovered in urine+feces+emesis (if any); (2) $< 1\%$ of radioactive dose has been recovered in urine+feces during 24H interval over 2 consecutive days; (3) participant has reached Day 21 (in Period 1). At the latest, Period 2, Day -1 would occur on the same day as Period 1, Day 21.

Regimen A in Period 1: An oral dose of 300 mg PF-06865571 containing approximately 300 nCi ^{14}C (ie, radiolabeled PF-06865571).

Regimen B in Period 2: An oral dose of 300 mg unlabeled PF-06865571 followed at T_{max} by an IV dose of 300 nCi $[^{14}\text{C}]$ in 100 μg of PF-06865571 (3 $\mu\text{Ci}/\text{mg}$ active drug).

Screening will occur within 42 days of the first dose of the investigational product in Period 1. All participants will provide informed consent and undergo screening evaluations to determine their eligibility.

Eligible participants will be admitted to the CRU on Day -1 of Period 1 and scheduled to remain in the CRU through the completion of Period 2. As such, inpatient stay will be for a total duration of 12 days (minimum) to 25 days (maximum). Each participant will have 1 follow-up phone call that will occur at least 28 days and up to 35 days following the last dose of investigational product to assess for AEs and SAEs.

A participant is considered to have completed the study if he has completed all phases of the study, including the last scheduled procedure as mentioned in the Schedule of Activities in the study protocol.

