8. STATISTICAL METHODOLOGY AND STATISTICAL ANALYSES

8.1. Statistical Methods

Precision of the estimate of PK parameters will be determined by constructing 90% confidence intervals around the estimated difference between the Test and Reference treatments using a mixed effects model based on natural log transformed data. The mixed effects model will be implemented using SAS Proc Mixed, with REML estimation method and Kenward-Roger degrees of freedom algorithm.

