8.2.3.3.2. Calculation of Fa

Fa will be estimated as the ratio of the adjusted geometric means of % of administered radioactive dose excreted into the urine following oral and IV administration of [^{14}C]PF-06865571 microtracer dose over the same collection time (up to 48 hours post dose) in Periods 1 and 2, respectively:

$$\text{Fa} = [\%^{14}\text{C}_\text{Urine_PO}/\%^{14}\text{C}_\text{Urine_IV}]$$

Geometric mean ratio and 90% confidence interval: Natural log transformed % Total ^{14}C in Urine from Period 1 and Period 2 will be analyzed using a mixed effect model with treatment as a fixed effect and participant as a random effect. Estimates of the adjusted (least squares) mean differences (Test-Reference) and the corresponding 90% CI will be obtained from the model. The adjusted mean differences and 90% CIs for the differences will be exponentiated to provide estimates of the ratio of adjusted geometric means (Test/Reference) and 90% CI for the ratio. Total ^{14}C _Urine_IV is the Reference formulation and Total ^{14}C _Urine_PO is the Test formulation.

Theoretically Fa would be expected to be greater than F. In the event that F is estimated to be greater than Fa, the greater of the 2 values will be used to represent the fraction of PF-06865571 absorbed. PF-06865571 will be considered highly permeable if either F or Fa is greater than 0.85.

PK parameters will be summarized by treatment and analyte as specified in Table 2.

Table 2. PK Parameters to be Summarized Descriptively

Matrix	Parameter	Summary Statistics
Plasma	AUC _{last} , AUC _{last(dn)} , AUC _{inf} , AUC _{inf(dn)} , C _{max} , C _{max(dn)} , F, [CL/F (oral) or CL (IV)] and [Vz/F (oral) or V _{ss} (IV)]	N, arithmetic mean, median, cv%, standard deviation, minimum, maximum, geometric mean and geometric cv%.
Plasma	T _{max}	N, median, minimum, maximum.
Plasma	t _{1/2}	N, arithmetic mean, median, cv%, standard deviation, minimum, maximum.
Urine	Total ^{14}C Urine PO, Total ^{14}C Urine IV, % ^{14}C Urine PO, % ^{14}C Urine IV, Fa	N, arithmetic mean, median, cv%, standard deviation, minimum, maximum.

Box and whisker plots for individual participant parameters (AUC_{inf(dn)}, AUC_{last(dn)}, C_{max(dn)}, % ^{14}C urine PO, and % ^{14}C urine IV) be presented and overlaid with geometric means.

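### The sign of the oral-IV covariance in 4 to 6 men decides whether the 90% CI for F and Fa is paired or unpaired, so overall coverage can fall below 90%; the printed RANDOM line is also invalid

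*SAP*

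**What the plan says.** SAP 8.1 sets the method: "The mixed effects model will be implemented using SAS Proc Mixed, with REML estimation method and Kenward-Roger degrees of freedom algorithm". SAP 8.2.3.3.2 applies it to Fa, where the log percentage of dose in urine "will be analyzed using a mixed effect model with treatment as a fixed effect and participant as a random effect"; SAP 8.2.3.2 does the same for F with dose-normalised AUC. Appendix 1 gives the only model code. It is introduced as an example for plasma data, but its treatment letters cover both F and Fa. The random effect is written "random participant /participant=participant" and the interval comes from "estimate 'Test vs Reference' trt -1 1 /cl alpha=0.1". No NOBOUND option is printed, and the SAP has no rule for a participant variance estimated as zero.

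Protocol 4.2 explains the two-period design as allowing a within-participant "comparison of the urinary excretion of radioactivity with both routes for the estimation of Fa". On numbers, SAP 2.1 says "6 participants will be enrolled to ensure evaluable data is acquired in at least 4 participants", and Protocol 9.2 says of the choice of six: "This sample size was not chosen based on any empirical data or hypothesis testing criteria".

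**The concern.** Each man contributes one oral and one IV value, so the design calls for a paired comparison. A random-intercept model delivers it only if the estimated participant variance is above zero. With 4 to 6 men, that estimate can easily be zero when the true correlation is weak. The model then treats the oral and IV values as independent samples, and the SAP does not say so. Choosing between two intervals by looking at the data generally spoils the stated confidence level. At stake is whether the 90% attached to F and Fa is right, and whether the within-man comparison is kept.

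The code also needs attention. `participant=` is not an option of the RANDOM statement; SUBJECT= appears to have been overwritten by a search-and-replace. The `ods ... out=` lines lack the usual ODS OUTPUT form. As printed, the step should not run. This rests on standard SAS syntax; SAS was not run.

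**Working it through.** **Inputs.** From the documents: n = 6 enrolled with a target of at least 4 evaluable (SAP 2.1), a 90% CI, REML with Kenward-Roger, participant random. The only stated figure to check is the confidence level: alpha = 0.1 gives 1 − 0.1 = 90%, which agrees. Assumed, because the documents are silent: the true oral-IV correlation ρ (−0.5 to 0.9 shown), equal log-scale SDs, complete pairs, default lower bound of 0, and 2n − 2 degrees of freedom once the variance is set to zero.

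**Algebra.** Let Sxx and Syy be the sample variances of the two log values and Sxy their covariance. With complete pairs, unbounded REML gives participant variance = Sxy and residual variance = (Sxx + Syy)/2 − Sxy.

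- Sxy > 0: SE = √[(Sxx + Syy − 2Sxy)/n], df = n − 1. This is the paired t interval.
- Sxy ≤ 0: participant variance is set to 0 and SE = √[(Sxx + Syy)/n]. This is the unpaired interval.

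A numerical bounded REML fit at n = 6 confirms both SEs. With Sxy < 0 the participant variance was 0 and the SE 0.0718 (unpaired formula 0.0718, paired 0.0853). With Sxy > 0 the SE was 0.0280 (paired formula 0.0280).

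**Width.** The t multiplier falls from 2.353 to 1.943 at n = 4, and from 2.015 to 1.812 at n = 6. With equal sample variances and sample correlation r, the log-scale width ratio (unpaired/paired) is t(2n−2) / [t(n−1) × √(1 − r)]. At n = 6, r = −0.4 this is 1.812/(2.015 × 1.183) = 0.76; at n = 4 it is 0.70.

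Example with assumed log SD 0.20, n = 6, r = −0.3 and Fa = 0.90:

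- Paired: SE = √(0.08 × 1.3/6) = 0.132; 0.90 × exp(±2.015 × 0.132) = 0.69 to 1.17.
- Bounded model: SE = √(0.08/6) = 0.115; 0.90 × exp(±1.812 × 0.115) = 0.73 to 1.11.

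**Coverage.** 400,000 simulated trials per setting; each cell shows n = 4 / n = 6.

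| True ρ | Bound hit, % | Overall coverage, % | Coverage when bound hit, % | Overall if df stay n − 1, % |
|---|---|---|---|---|
| −0.5 | 81 / 87 | 82.0 / 82.1 | 84.5 / 83.6 | 86.7 / 85.4 |
| −0.3 | 69 / 74 | 84.1 / 84.5 | 87.1 / 86.6 | 87.7 / 87.0 |
| 0 | 50 / 50 | 86.6 / 87.2 | 90.0 / 89.9 | 88.8 / 88.6 |
| 0.3 | 31 / 26 | 88.4 / 88.9 | 92.0 / 92.5 | 89.6 / 89.5 |
| 0.5 | 20 / 13 | 89.1 / 89.5 | 92.9 / 93.8 | 89.7 / 89.8 |
| 0.9 | 2 / 0.3 | 89.9 / 90.0 | 94.4 / 95.5 | 90.0 / 90.0 |

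Further runs gave about 88 to 88.5% overall at ρ = 0.2 and about 89% at 0.4. The paired t interval used throughout covered about 90% in every setting.

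**Source of the shortfall at ρ = 0, n = 6.** Overall coverage 0.8715 = 0.5003 × 0.8994 + 0.4997 × c, so c = 0.844. The intervals reported as unpaired cover 90%. The loss sits in the paired intervals, which are kept only when the sample covariance happens to be positive.

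**The case against.** A reader might infer that every interval produced at the bound is too narrow. The documents do not support that. They give no correlation, and at a true correlation of 0 or more with equal SDs those intervals cover 90% or more, although they are narrower than the paired ones. Bound-hit intervals fall clearly short only if the true correlation is negative. With an SD ratio of 2 the loss is about 1 point at ρ = 0 (88.8% / 89.1% for n = 4 / 6).

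Other objections stand in part:

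- **No decision uses the interval.** No hypothesis is tested, and the 0.85 permeability statement in SAP 8.2.3.3.2 is worded on F or Fa itself. With complete pairs the bound leaves the estimate unchanged.
- **The CI is not the only account of spread.** SAP Table 2 also summarises F and Fa with SD and cv%.
- **F is little affected.** Both AUCs come from the same man in the same period and share his clearance, so a positive correlation is expected. Fa is more exposed, because its two urine values come from different periods.
- **The degrees of freedom at the bound are an assumption about SAS.** If they stay at n − 1, the loss at ρ = 0 is about 1 point rather than 3.
- **The code is labelled an example, and an invalid option would stop with an error.** It could not silently give a wrong result, so by itself it is clerical.

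None of this removes the selection effect or supplies the missing rule for a zero variance.

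**Conclusion.** The point holds as a minor one. The planned model does not fix in advance whether the reported 90% CI is paired or unpaired, and overall coverage falls below 90% as a result. With equal SDs, complete pairs and 2n − 2 degrees of freedom at the bound, the loss is about 3 points at a true correlation of 0, about 6 points at −0.3, and under 1 point at 0.5 and above. The true correlation is unknown, so where the trial lies in that range cannot be settled from the documents. The consequence is confined to reported precision, mainly for Fa.

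**What to change.** In Appendix 1, add NOBOUND to the PROC MIXED statement and replace the RANDOM line with `random intercept / subject=participant`. Alternatives are `repeated trt / subject=participant type=un` with `ddfm=KR`, or a prespecified paired-t 90% CI on the within-man log differences. Correct the ODS lines in the same edit, and state in SAP 8.1 which form applies to F and Fa.

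The NOBOUND form is preferable to the paired t. SAP 7.3 sets non-calculable parameters to missing and still allows the model when up to half are missing. A paired t would drop a man with only one value, while the mixed model keeps him, so the two could then give different estimates.

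The cost is a few lines of code. With complete pairs nothing changes when the sample covariance is positive. When it is zero or negative the CI is wider: for true correlations of 0 to 0.5, the bounded interval's median width was 0.70 to 0.73 of the paired one at n = 4 and 0.79 to 0.82 at n = 6. Some of the intervals widened would already have covered 90% or more; that is the price of a rule whose coverage is 90% overall.
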